**1.0 INTRODUCTION**

Title	Definitive Re-Irradiation with Proton Beam Radiotherapy for Patients with Recurrent Thoracic Cancers
Short Title	Proton Re-Irradiation in the Thorax
Protocol Number	
Phase	Pilot Study
Methodology	Single Arm Open-Label
Study Duration	3 years
Study Center(s)	University of Washington Medical Center/SCCA Procure Proton Center
Objectives	To utilize proton radiation to safely treat patients with tumors in the thorax, who have previously received radiation to the chest. We will assess the efficacy and toxicity of treatment.
Number of Subjects	20 evaluable subjects
Diagnosis and Main Inclusion Criteria	Patients diagnosed with tumors in the thorax, who have previously received radiation to the chest, such that the current radiation treatment fields are likely to overlap with the prior radiation fields.
Study Product, Dose, Route, Regimen	Proton radiation to the thorax
Duration of administration	Radiation treatment regimens will be at the discretion of the treating radiation oncologist, BED2Gy at least 60 Gy
Statistical Methodology	We expect to see <25% grade 3 toxicity attributable to radiation, and ≥80% local tumor control at 3-months post-treatment

This document is a protocol for a human research study. This study is to be conducted according to US and international standards of Good Clinical Practice (FDA Title 21 part 312 and International Conference on Harmonization guidelines), applicable government regulations and Institutional research policies and procedures.

**2.0 BACKGROUND****2.1 Study Disease**

Lung cancer is the most common cause of cancer related mortality in the US. Radiation therapy is a main treatment modality for lung cancer: for resectable tumors, radiation can be given pre-operatively or post-operatively to improve local tumor control and outcomes; for unresectable tumors, radiation can be given as definitive treatment for the cancer, either alone or in combination with chemotherapy.

Local recurrence remains a significant cause of treatment failure in lung cancer. For stage III lung cancer treated with definitive chemoradiation, local failure rates range from 30% to 50% [1, 2]. At the time of lung cancer recurrence, patients often present as a heterogeneous group, with a mixture of local as well as systemic disease, and varying time intervals to recurrence. Outcomes are generally poor with recurrence, however, various treatments are often given to either prolong life or palliate symptoms. Depending on specific patient characteristics such as age, stage, histology, and performance status, aggressive treatments can sometimes be pursued with superior outcomes to supportive care alone.

External beam radiation is often given to patients with recurrent lung cancer to provide local tumor control and palliate symptoms. This can be challenging in patients who have previously received

radiation to the chest, usually as part of the initial cancer treatment. Radiation oncologists are guided by normal tissue tolerances, which is the standard of care radiation dose that is felt to be safe for specific organs in the body. Typically, for patients who have already received thoracic radiation, many organs in the area have already received a significant radiation dose. Therefore, it is often assumed that thoracic radiation cannot be repeated. Even when repeat radiation is given, it is typically for palliative doses, due to concerns about toxicity if higher radiation doses were attempted, as well as concerns over patient life expectancy [3].

Recent technological advances in radiation therapy and imaging have led to more interest and more feasibility in the role of repeat radiation for a select group of recurrent cancer patients. For patients with symptomatic locally recurrent tumors, or patients with good systemic disease control but persistent or progressive local disease, repeat radiation with moderately high radiation doses can provide lasting tumor control and symptom palliation. Multiple clinical series have been published on thoracic re-irradiation, showing safety and efficacy [4-10]. However, the series are typically retrospective or prospective registry trials, with no prospective guidelines in terms of radiation dose limits for normal organs. Radiation doses and fractionation varies widely. Toxicity and efficacy information are often incomplete. Table 1 summarizes some of the best published clinical data on repeat irradiation in the thorax. As systemic treatments improve for lung cancer, local control will also become more critical for this patient population, and prospective guidelines to safely deliver repeat radiation must be developed.

**Table 1. Summary of Recurrent Thoracic Radiation**

Study	Institution	# of patients	Radiation Technique	Toxicity	Local Control
Kelly et al. IJROBP 2010[8]	MD Anderson	36	SBRT (10 Gy x4 fractions or 10 Gy x5)	33% grade 3. No grade 4 or 5.	92% at 2 years
Trakul et al. JTO 2012[9]	Stanford	17	SBRT (dose fractionation varies)	13% grade 3. No grade 4 or 5.	65.5% at 1 year
Seung et al. J Cancer Therapy 2011[10]	Oregon Clinic	8	SBRT (8-20 Gy x3-5 fractions)	100% grade 2 pneumonitis. No grade 3 or higher.	86% at 1.5 years

In addition to recurrent lung cancers, other malignancies can also result in the need for repeat irradiation of the chest. For example, recurrent thymomas that were previously treated with radiation therapy can still have a relatively long disease course. In unresectable localized recurrences that show no evidence of dissemination, in patients with good performance status and life expectancy, it would be reasonable to consider repeat radiation. Patients with one thoracic cancer can also develop a second primary malignancy in the chest (i.e. esophageal cancer that was treated with radiation years ago, now with lung cancer; or breast cancer treated previously, now with lung cancer). Since radiation planning is guided by normal organ dose limits, this patient population would follow similar radiation guidelines as recurrent lung cancer patients, in terms of normal organ radiation constraints.

## 2.2 Rationale for Use of Proton Radiation

Proton radiation has unique physical properties compared with photon-based radiation due to the Bragg peak[11]. For the more widely available photon-based radiation, the radiation beams enter the

patient's body, deposits energy and causes tissue damage, and exists through the body on the other side. In comparison, proton radiation beams enter a patient's body, deposits a relatively small amount of energy along the path, until the beam weakens to the point when it deposits all of its energy immediately before the proton particles come to rest. This is called the Bragg peak. This physical characteristic of proton therapy has the potential for less normal tissue exposure to radiation, and therefore less toxicity. Multiple publications have shown that proton radiation have superior normal tissue sparing compared with photon-based radiation [12-14].

### 2.3 Clinical Data to Date

Proton radiation has been increasingly used for treating lung and other thoracic malignancies in the recent years, with multiple published patient series showing safety and efficacy [15-17]. Multiple clinical series have also been published on thoracic re-irradiation, showing safety and efficacy [4-7]. However, the series are typically retrospective or prospective registry trials, with no prospective guidelines in terms of radiation dose limits for normal organs. Radiation doses and fractionation varies widely. Toxicity and efficacy information are often incomplete.

### 2.4 Risks/Benefits

The benefit for patients enrolled in this trial is to receive proton radiation treatment to the thorax for recurrent tumors, which adheres to strict radiation normal organ dose limits that has been developed after thorough literature review and multiple radiation oncology specialists.

The potential harm for patients enrolled in this trial is the radiation toxicity related to re-irradiation.

## 3.0 STUDY OBJECTIVES

### 3.1 Primary Objective

To assess the grade 3 toxicity associated with thoracic re-irradiation with proton therapy, with prospectively applied normal organ radiation dose limits.

Hypothesis: With the normal tissue dose limits listed in this protocol, repeat radiation to the chest can be delivered safely without grade 3 or greater toxicity exceeding 25%.

### 3.2 Secondary Objective

To assess the efficacy of thoracic re-irradiation with proton therapy.

Hypothesis: We will achieve >80% local tumor control at 3-months post-treatment inside the radiation field.

## 4.0 STUDY DESIGN

### 4.1 General Design

This is a pilot study to utilize proton radiation to safely treat patients with tumors in the thorax, who have previously received radiation to the chest. We have set out specific radiation guidelines for normal tissue dose limits and tumor coverage.

### 4.2 Endpoints

#### 4.2.1 Primary Endpoint

Grade 3 or greater toxicity attributable to radiation treatment.

#### 4.2.2 Secondary Endpoint

- Local control (Failure: tumor progression per RECIST criteria – at least a 20% increase in the sum of the LD of target lesions, taking as reference the smallest sum LD recorded since the treatment started or the appearance of one or more new lesions inside the full dose radiation field.)
- Overall survival (Failure: death due to any cause)
- Grade 2 toxicity attributable to radiation treatment

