## 5.0 SUBJECT SELECTION

### 5.1 Inclusion Criteria

- 5.1.1 Patients >18 years old.
- 5.1.2 Women of child-bearing age must have a negative pregnancy test.
- 5.1.3 Patients must have received prior radiation treatment to the chest. Records of prior radiation treatment must be available.
- 5.1.4 Patients must have received prior chest radiation at least 3 months prior to enrollment in this trial. Radiation treatment to other body sites not overlapping with current radiation fields are allowed within the 3 months period (example, brain radiation is allowed).
- 5.1.5 Patients must have a prior diagnosis of cancer inside the thoracic cavity. Both primary thoracic malignancies (such as lung cancer) as well as metastatic lesions (such as metastatic breast cancer or colorectal cancer to the lungs) are allowed. Patient must have pathologic confirmation of the recurrent thoracic tumor, or have an enlarging thoracic mass (as seen on two CT scans at least 6 weeks apart, with either a >25% or >5 mm increase in longest dimension).
- 5.1.6 Patients must have a life expectancy of > 6 months.
- 5.1.7 Patients must have measurable disease to be treated with proton radiation (minimum tumor dimension at least 10 mm on CT imaging).
- 5.1.8 Patients should have either non-metastatic cancer of the thorax, or metastatic cancer to the thorax and candidate for definitive radiation dose to the thoracic tumor (not palliative intent), tumor radiation dose to at least BED2Gy 60 Gy.
- 5.1.9 Patients must be able to receive proton radiation treatment.
- 5.1.10 All stages of cancer are eligible.
- 5.1.11 There are no limits on prior therapy. Patients are allowed to have prior chemotherapy and surgery. Patients are allowed to have concurrent chemotherapy with radiation treatment. Patients are allowed to have chemotherapy or surgery after radiation treatment.
- 5.1.12 Patients are allowed to be on another study concurrent with this protocol.
- 5.1.13 Ability to understand and the willingness to sign a written informed consent document.

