## 7.1 Radiation Treatment Parameters

### 7.1.1 Localization, Simulation, and Immobilization

Body cradle or similar immobilization device(s) must be utilized. A treatment planning CT scan is mandatory. CT scan thickness should be 0.5 cm or smaller (preferably  $\leq 0.3$  cm) through the treatment volume. Intravenous contrast is recommended in patients who do not have a contraindication to it. MRI and/or PET scans with image fusion also may be helpful in treatment planning, particularly if these scans can be performed with the same immobilization device as was used for the planning CT scan. 4D CT scan with respiratory motion tracking is strongly preferred for lung tumors. Any tumors moving more than 1 cm with respiration must be considered for motion management for radiation treatment, which can include but not limited to: abdominal compression, respiratory gating, and active breathing control. These are all standard of care for lung radiation treatment.

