## 9.0 ASSESSMENT OF EFFICACY

### 9.1 Efficacy Parameters

Tumor response will be assessed using the RECIST criteria.

For tumors targeted by radiation:

- Complete Response (CR): Disappearance of all target lesions
- Partial Response (PR): At least a 30% decrease in the sum of the LD of target lesions, taking as reference the baseline sum LD
- Stable Disease (SD): Neither sufficient shrinkage to qualify for PR nor sufficient increase to qualify for PD, taking as reference the smallest sum LD since the treatment started
- Progressive Disease (PD): At least a 20% increase in the sum of the LD of target lesions, taking as reference the smallest sum LD recorded since the treatment started or the appearance of one or more new lesions

Patients with a global deterioration of health status requiring discontinuation of treatment without objective evidence of disease progression at that time should be classified as having "symptomatic deterioration". Every effort will be made to document the objective progression even after discontinuation of treatment.

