### 9.2 Method and Timing

Tumors will be measured on axial CT chest images. The radiation treatment planning scan will be used as baseline. The 3-months post-treatment scan will be used for comparison.

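### Local failure is called on a 20% rise in sum LD with no millimetre minimum, from one post-treatment CT, so 2 mm of growth fails a lone 10 mm target

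*Combined protocol and SAP*

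**What the plan says.** Section 4.2.2 defines local failure by RECIST, without naming a version, and writes the rule out: "at least a 20% increase in the sum of the LD of target lesions, taking as reference the smallest sum LD recorded since the treatment" began, or "the appearance of one or more new lesions inside the full dose radiation field". Section 9.1 gives the same threshold for tumors targeted by radiation: "Progressive Disease (PD): At least a 20% increase in the sum of the LD of target lesions". Neither section adds an absolute minimum, a confirmation step, or a way to classify in-field change that could be tumor or radiation effect.

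Section 9.2 measures on axial CT and takes the planning scan as baseline. For follow-up it says: "The 3-months post-treatment scan will be used for comparison". The footnote to the study calendar (Table 2) lets that visit fall anywhere from 2 to 6 months. Section 7.0 leaves later imaging to routine care and has research staff review the record at 3 months.

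Section 5.1.7 sets the smallest eligible tumor: "minimum tumor dimension at least 10 mm on CT imaging". Section 5.1.5, for entry without pathology, asks for more than 25% or more than 5 mm of growth on two CTs at least 6 weeks apart.

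Section 10.0 gives local control its own verdict counts in 20 patients: 18 or more is favorable, 14 or fewer is unfavorable, and 15 to 17 is inconclusive.

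**The concern.** A purely relative threshold gets smaller in millimetres as the tumor gets smaller. For the smallest eligible tumors the plan calls failure on a change of 2 to 3 mm, from a single comparison of two scans that are not required to match in technique. The protocol is stricter when growth alone admits a patient (section 5.1.5) than when growth ends local control.

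The missing rule for in-field opacity adds a second route to misclassification. Opacity that lengthens the measured LD, or is read as a new in-field lesion, can be scored as failure, and nothing written tells the reader how to handle doubt.

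Both routes push observed local control down. The endpoint is secondary, but with 20 patients one misread scan moves 18 of 20 from favorable to inconclusive.

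**Working it through.** **1. The plan's own figures.** Exact binomial, n = 20, true control 80%:
- P(X ≥ 18) = 0.206, so 18 of 20 gives 79.4% confidence that the rate exceeds 80%.
- P(X ≤ 14) = 0.196, so 14 of 20 gives 80.4% confidence that it is below 80%.

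Section 10.0 states at least 80% for each, so its counts reproduce to within a point.

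**2. The trigger in millimetres.** Trigger = 0.20 × sum LD.

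| Sum LD (mm) | 10 | 15 | 20 | 25 | 30 |
|---|---|---|---|---|---|
| Trigger (mm) | 2 | 3 | 4 | 5 | 6 |

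A 5 mm minimum therefore changes the rule only below 25 mm. With one follow-up scan, the smallest-sum reference is in practice the planning scan.

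**3. False progression in an unchanged tumor.** The documents give no measurement error. Assume a normally distributed scan-to-scan difference with mean 0 and SD s, for a lone target of length L.
- Bare rule: 1 − Φ(0.20L / s)
- With the minimum: 1 − Φ(max(0.20L, 5) / s)

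Example: L = 10, s = 2 gives 1 − Φ(1) = 15.9% for the bare rule and 1 − Φ(2.5) = 0.6% with the minimum.

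| Assumed SD (mm) | 1 | 1.5 | 2 | 3 |
|---|---|---|---|---|
| 10 mm, bare 20% | 2.3% | 9.1% | 15.9% | 25.2% |
| 15 mm, bare 20% | 0.1% | 2.3% | 6.7% | 15.9% |
| 20 mm, bare 20% | <0.1% | 0.4% | 2.3% | 9.1% |
| 10, 15 or 20 mm, with 5 mm minimum | <0.1% | <0.1% | 0.6% | 4.8% |

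**4. Effect on the section 10.0 verdict.** Let f be the share of truly controlled patients scored as failures, from either route (assumption). Observed control = 0.90 × (1 − f) when true control is 90%.

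| f | Observed control | P(18 or more of 20) | P(14 or fewer of 20) |
|---|---|---|---|
| 0% | 90.0% | 67.7% | 1.1% |
| 2% | 88.2% | 57.4% | 2.4% |
| 5% | 85.5% | 43.0% | 5.9% |
| 10% | 81.0% | 23.9% | 16.4% |

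**5. The opposite error.** Suppose unconfirmed progression were counted as controlled, and true control were 80%. If 25% of true failures went unconfirmed, observed control would be 0.80 + 0.25 × 0.20 = 85%, and P(18 or more) would rise from 20.6% to 40.5%. If 50% went unconfirmed, observed control would be 90% and P(18 or more) 67.7%.

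**The case against.** The strongest reply is that the size of the problem rests on assumptions. The documents give neither the measurement error nor the mix of tumor sizes. The 2 mm trigger is the extreme case, the minimum matters only below 25 mm, and step 3 assumes a tumor that has not shrunk after definitive-dose treatment. The endpoint is secondary in a pilot, no stopping rule depends on it, and from 18 of 20 it takes four false failures to reach the unfavorable zone. All of this stands. It limits the size of the effect; it does not supply the missing minimum. RECIST cited without a version could carry a further condition by reference, but the rule written out in two sections contains none.

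A reader might infer more than the documents support:
- **That radiation change counts as progression.** No section says so. Failure is defined on target lesions and new lesions. The gap is that nothing tells the reader how to exclude radiation change.
- **That 2 to 5 mm is within measurement noise.** Section 7.1.1 says "CT scan thickness should be 0.5 cm or smaller" and prefers 0.3 cm or less, but slice thickness is through-plane, while LD is read in-plane on axial images. It does not establish the LD error.
- **That false failures from pneumonitis are expected and tie efficacy to the primary endpoint.** One Table 1 row reports "100% grade 2 pneumonitis. No grade 3 or higher", but in 8 patients treated with SBRT, and the same row gives 86% local control at 1.5 years. It makes lung change plausible and supplies no rate of misread scans. The primary endpoint is grade 3 or greater toxicity, which that series did not have.
- **That unconfirmed change should be scored as controlled.** Later imaging is optional, record review is set at 3 months, and section 5.1.11 allows chemotherapy or surgery after radiation, which could hide true failures. Step 5 shows how far that would bias control upward.

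**Conclusion.** The concern holds as a gap in the endpoint definition. The bare 20% rule puts the failure trigger at 2 mm for a lone 10 mm target and below 5 mm for any sum LD under 25 mm; this follows from the documents alone. The plan also has no rule for indeterminate in-field change.

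The consequences are conditional. Under the assumed SDs of 1 to 3 mm, an unchanged 10 mm tumor is called progressed about 2% to 25% of the time, and a 5 mm minimum brings this to between under 0.1% and about 5%. At an assumed true control of 90%, false progression in 5% or 10% of controlled patients cuts the chance of a favorable verdict from 68% to 43% or 24%. These overall rates need enough small tumors, enough measurement error, or some misread radiation change; with mostly larger tumors the loss is smaller. The change is worth making because it is cheap and each patient carries weight in a sample of 20.

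**What to change.** In sections 4.2.2 and 9.1, require a rise in sum LD of at least 20% and at least 5 mm, and name the RECIST version.

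Add a rule for in-field change. Change that meets the failure definition stays a failure in the main count even if unconfirmed. The reader flags in-field change judged indeterminate between tumor and radiation effect. Report a sensitivity count with the flagged patients as controlled, using later routine CT, PET or pathology to resolve cases where these exist.

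Cost: endpoint wording, with no added procedures. Record review must extend beyond the 3-month review in section 7.0 to any later routine scan. The trade-off is that a small true progression in a tumor under 25 mm may be missed on the 3-month scan: a 10 mm target would have to reach 15 mm, and a 20 mm target 25 mm, before growth alone counts as failure.

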### 7.1.2 Volume Definitions

**Gross Tumor Volume (GTV):** This is the region of interest that is known to contain gross cancer. This will include all gross tumor as based upon the planning CT scan. This also may include areas that appear “normal” by the planning CT scan but are known to harbor cancer based on the MRI, PET, physical examination, endoscopy, etc.

**Clinical Tumor Volume (CTV):** The CTV is defined to be the GTV plus a margin as appropriate to account for microscopic tumor extension. The exact CTV margin to be used is at the discretion of the treating physician, and can be as low as 0 mm if microscopic extension is not felt to be of concern in a particular patient situation.

**Internal Target Volume (ITV):** If 4D CT scans are used to assess for breathing motion, the ITV will be used to encompass the CTV and all respiratory motion.

**Planning Tumor Volume (PTV):** This includes the CTV (or ITV if appropriate) plus a margin to compensate for various uncertainties, such as systematic treatment setup variables, organ motion (especially with respiratory motion), and organ displacement. A minimum of 5 mm around the CTV is required in all directions, except where the CTV is immediately adjacent to a critical organ such as the spinal cord (in which case, the margin from CTV to PTV may be as small as 1 mm).

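### Local failure has no trigger for progression of known irradiated disease outside the CT-measured sum, so such progression counts as local control unless it is read as a new lesion

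*Combined protocol and SAP*

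**What the plan says.** Section 4.2.2 defines failure of local control as progression per RECIST and then writes the rule out. One trigger is growth in diameter: "at least a 20% increase in the sum of the LD of target lesions, taking as reference the smallest sum LD recorded since the treatment" began. The other is "the appearance of one or more new lesions inside the full dose radiation field". Section 9.1 gives the same pair for progressive disease ("At least a 20% increase in the sum of the LD of target lesions, taking as reference the smallest sum LD recorded since the treatment" began, or a new lesion). It defines complete response, partial response and stable disease on target lesions alone. Stable disease, for example, is "Neither sufficient shrinkage to qualify for PR nor sufficient increase to qualify for PD, taking as reference the smallest sum LD since the treatment started". The list is headed "For tumors targeted by radiation", but target lesion is not defined further and there is no category for disease outside the sum.

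Section 9.2 sets the method: "Tumors will be measured on axial CT chest images", and "The radiation treatment planning scan will be used as baseline", to be compared with the 3-month scan.

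Section 7.1.2 draws the irradiated gross tumor volume more widely than CT can see. It may take in areas that look normal on the planning CT but "are known to harbor cancer based on the MRI, PET, physical examination, endoscopy, etc". Section 5.1.7 requires measurable disease of at least 10 mm on CT; it does not exclude further disease that cannot be measured.

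**The concern.** The irradiated volume and the assessed volume need not coincide. A patient can enter with one measurable mass plus other irradiated gross disease that is visible but not measured, or that is known only from PET, MRI or endoscopy. If the second component progresses while the mass shrinks, neither written trigger is met: the measured sum has not grown, and disease known at baseline is not obviously new. The documents define failure only, so whatever is not failure is counted as control.

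That does not fit objective 3.2, which is about control of tumor within the radiation field. The error can run in one direction only, from failure to control. It feeds the Section 10 count, where 18 or more of 20 is read as control above 80%, 14 or fewer as control below 80%, and 15 to 17 as inconclusive.

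**Working it through.** **1. The rule applied to a constructed case.** Take a 25 mm measured mass plus endobronchial tumor seen only at endoscopy, both in the GTV. At follow-up the mass is 20 mm and endoscopy done in routine care shows that the endobronchial tumor has progressed.
- Change in the sum: (20 − 25)/25 = −20%. A rise to 25 × 1.2 = 30 mm or more was needed for failure.
- Partial response needs a 30% fall, so Section 9.1 returns stable disease.
- New lesion: the endobronchial tumor was known at baseline, so on a plain reading it is not new.
- Result: no failure, hence control.

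The symptomatic-deterioration label in Section 9.1 does not change this. It is for patients without objective evidence of progression, and it is not named as local failure.

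**2. The plan's own cut-offs.** Inputs from Section 10: n = 20, reference rate 80%, cut-offs 18 and 14. Exact binomial:
- P(X ≥ 18 | 0.80) = 190(0.8^18)(0.2^2) + 20(0.8^19)(0.2) + 0.8^20 = 0.1369 + 0.0576 + 0.0115 = 0.206, so confidence is 79.4%.
- P(X ≤ 14 | 0.80) = 0.196, so confidence is 80.4%.

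The first is marginally under the stated 80% by the exact method. Mid-p, score, Wald and uniform-prior posterior calculations give 82.1% to 93.2% across the two cut-offs. Under every one of these methods 17 and 15 fall below 80%, so the cut-offs are taken as they stand.

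**3. Effect of one patient.** Moving one true failure to control turns 17 into 18 (exact confidence that the rate exceeds 80%: 58.9% to 79.4%), or 14 into 15 (exact confidence that it is below 80%: 80.4% to 63.0%). Either move changes the stated conclusion.

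**4. Illustration of size.** Let p be true in-field control and m the share of true failures scored as control. The documents do not give m; the values below are assumptions. Observed rate p′ = p + (1 − p)m, with X binomial(20, p′). Expected missed patients = 20(1 − p)m.

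| p | m | p′ | Missed patients | P(X ≥ 18) | P(X ≤ 14) |
|---|---|---|---|---|---|
| 0.80 | 0 | 0.800 | 0 | 20.6% | 19.6% |
| 0.80 | 10% | 0.820 | 0.4 | 27.5% | 13.6% |
| 0.80 | 25% | 0.850 | 1.0 | 40.5% | 6.7% |
| 0.80 | 50% | 0.900 | 2.0 | 67.7% | 1.1% |
| 0.75 | 0 | 0.750 | 0 | 9.1% | 38.3% |
| 0.75 | 10% | 0.775 | 0.5 | 13.9% | 28.4% |
| 0.75 | 25% | 0.8125 | 1.25 | 24.7% | 15.7% |
| 0.75 | 50% | 0.875 | 2.5 | 53.5% | 3.1% |

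The m = 0 rows suppose that every such progression is detected and scored as failure.

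**The case against.** Four arguments on the other side carry weight.

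- **RECIST is cited.** Sections 4.2.2 and 9.1 both invoke it, so the written triggers could be a shorthand for criteria adopted by reference. The documents neither name a version nor say which reading is meant. This leaves some room, but both sections write the rule out and stop at two triggers, and whoever scores the scans will most likely apply what is written.
- **Disease that CT could not show may later count as new.** The planning scan is the baseline. An area normal on that scan that becomes visible at 3 months can reasonably be called a new lesion, and hence a failure. This stands. It leaves disease visible but unmeasured at baseline, and progression that never shows on CT.
- **Every irradiated tumor may be a target lesion**, given the heading in Section 9.1. This is possible, but it does not say how a component that CT cannot measure would enter a sum of diameters.
- **Detection would often need unscheduled tests.** The study calendar lists examination, history, pulmonary function tests and CT chest at follow-up. Section 7.0 allows additional imaging and visits under standard of care and has staff review the clinical record, so the evidence can arise, but only in some patients. This also stands: an affected patient needs extra non-measured disease, progression there but not in the measured mass, and a test that shows it, all by the follow-up visit.

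A reader might infer that every progression of CT-occult disease is certain to be scored as control, or that the local control result is materially inflated. The documents support neither. The new-lesion route remains open for some of these cases, and no figure for the missed share is available.

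**Conclusion.** The point holds in a limited form. As written, progression of irradiated gross disease known at baseline but outside the measured sum is counted as local control unless it is read as a new lesion. The direction of the bias is clear: toward control.

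Its size is not established. Every patient has at least one measurable lesion, so only those with additional non-measured disease can be affected, and they are probably few. That one patient can cross a cut-off is arithmetic; how often this would happen is unknown. The 10% to 50% shares are illustrations only and should not be quoted as estimates. They also assume independent patients and, for the comparison with correct scoring, full detection.

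Severity is minor: local control is a secondary endpoint in a 20-patient pilot, and the stopping rule in Section 8.1 does not depend on it. It is still worth settling, because the scoring should be fixed before results are seen and the change is small.

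**What to change.** 1. Add to the failure definition in 4.2.2 and to progressive disease in 9.1: *or unequivocal progression, on evidence obtained in routine care, of irradiated gross disease (GTV) not included in the target-lesion sum.* Count it as local failure in Section 10.
2. State that disease normal on the planning CT that later becomes visible on CT in the full-dose field counts as failure.
3. At planning, mark each GTV component as measured or non-measured.

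The cost is a few sentences and one database field, with no added procedure and no change in sample size. There are three downsides. Judging what is unequivocal takes some discretion in an open-label study. Ascertainment will be uneven, because no test is added: progression that CT cannot show will be found only in patients who happen to have another examination, so the trigger recovers only part of what might be missed. The local control count may come out slightly lower.
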